2.2. Background

Narcolepsy is a severe sleep disorder involving the dysregulation of sleep-wake cycles that is primarily characterized by EDS and manifested with or without features of rapid-eye movement (REM) sleep dissociation (eg, cataplexy, hypnagogic or hypnopompic hallucinations, sleep paralysis), and disrupted nighttime sleep ([AASM 2014](#); [Boscolo-Berto 2012](#), [Dauvilliers 2007](#); [Dauvilliers 2012](#); [Nishino 2007](#); [Ruoff and Rye 2016](#); [Thorpy 2014](#)). Narcolepsy is a chronic neurologic condition with no cure identified to date and a demonstrated burden of illness that can have far-reaching impacts on an individual's health over time ([Ahmed 2016](#); [Plazzi 2018](#); [AASM 2014](#)). The worldwide prevalence of narcolepsy is estimated to be 0.02% to 0.067% ([Ohayon 2007](#)), and in the US, the disease afflicts approximately 1 in 2000 individuals ([Majid and Hirschkowitz 2010](#)).

The precise mechanism of action of sodium oxybate in narcolepsy is not known. It is hypothesized that its effects on cataplexy and EDS are mediated through neuropharmacologic, B-subtype of the gamma-aminobutyric acid receptor (GABABR)-mediated actions on noradrenergic and dopaminergic neurons, as well as on thalamocortical neurons ([Xyrem USPI 2020](#); [Pardi and Black 2006](#); [Mathivet 1997](#), [Lingenhoehl 1999](#); [Snead 2000](#)). Evidence from clinical trials have shown that sodium oxybate

increases delta (slow-wave or restorative) sleep and improves sleep continuity. Other effects include increases in brain acetylcholine, and depression of glucose utilization, but not oxygen consumption, in the brain (Pardi and Black 2006). XYWAV was developed as a mixture of 4 oxybate salts to substantially lower sodium content relative to the current Xyrem formulation.

The therapeutic benefits and safety of oxybate for treatment of cataplexy and EDS in narcolepsy have been demonstrated through extensive clinical trials and post-marketing experience using Xyrem, and in recent clinical trials with XYWAV. Specifically, the efficacy and safety of XYWAV has been demonstrated in a randomized, controlled clinical trial (Study 15-006) which resulted in the approval of XYWAV for the treatment of cataplexy or EDS in patients 7 years of age and older with narcolepsy ([XYWAV USPI 2020](#)). In addition, the magnitude of the food effects appears to be lower with XYWAV (compared to Xyrem); however, dosing instructions require the first nightly dosing to occur at least 2 hours after the last meal. The present study is conducted to provide additional open-label evidence to support that participants on current Xyrem therapy can effectively and efficiently convert from Xyrem to XYWAV in a safe manner, with minimal tolerability challenges and maintain effective disease control. A detailed description of the chemistry, pharmacology, efficacy, and safety of XYWAV is provided in the [Investigator's Brochure \(IB\)](#).

2.3. Benefit/Risk Assessment

A summary of the benefit-risk assessment for conducting Study JZP258-401 is provided in the subsections below.

2.3.1. Risk Assessment

Participants with narcolepsy who enroll in this study may encounter the following potential risks:

- Participants may experience worsening of disease control with XYWAV compared to Xyrem
- Participants may experience reduced tolerability for XYWAV compared with Xyrem
- Procedural risks during screening, including risks and/or discomfort associated with clinical laboratory assessments and electrocardiography.

2.3.2. Benefit Assessment

Participants with narcolepsy who enroll in this study may experience the following benefits:

- Participants may experience improved disease control with XYWAV compared to Xyrem
- Participants may experience improved tolerability for XYWAV relative to Xyrem
- Participants may experience improved dosing flexibility of XYWAV with regard to timing of food intake
- Participants switching from Xyrem to XYWAV may have reduced medical risks associated with high levels of sodium consumption

2.3.3. Overall Benefit : Risk Conclusion

Benefits to participants include receiving therapy that may potentially alleviate symptoms of narcolepsy, while contributing to the knowledge base and clinical experience of new therapeutics for narcolepsy. Additionally, participants may experience health benefits from receiving comprehensive physical examinations (PE), clinical monitoring and laboratory testing. Risks to participants include those associated with administration of XYWAV and are expected to be similar to those seen in prior clinical studies, as detailed in the IB. Additional risks include the potential need to discontinue any prohibited medications, and potential risks related to study procedures.

3. OBJECTIVES AND ENDPOINTS

Objectives	Key Endpoints
To describe the clinical experience of participants switching from Xyrem to XYWAV for the treatment of narcolepsy with or without cataplexy in terms of safety, tolerability, effectiveness, and treatment optimization.	
 • Adverse Events and Serious Adverse Events • Change in the Nausea Visual Analog Scale • Change in weekly rate of cataplexy attacks (for Narcolepsy Type 1) • Change in Epworth Sleepiness Scale to assess excessive daytime sleepiness • Participant Global Impression of Change • Time to optimized dose and regimen • Number of changes from first dose and regimen to optimized dose and regimen • Number of participants dosing fasted versus dosing without consideration of food • Timing and characterization of meals relative to dosing
Exploratory Objectives	Exploratory Endpoints
To describe the ease of conversion and participant preference of XYWAV in participants with narcolepsy with or without cataplexy	
 • Ease of Switching Medications Scale • Forced Preference Questionnaire

4. STUDY DESIGN

Study JZP258-401 is an open-label, single-arm, phase 4 clinical study designed to describe the overall clinical experience in participants with narcolepsy transitioning treatment from Xyrem to XYWAV.

4.1. Overall Design

The open-label, single-arm, interventional design of Study JZP258-401 is intended to provide descriptive assessments of safety, tolerability, effectiveness and optimization of treatment during participant transition from Xyrem to XYWAV. The dosing information obtained in this trial may be used to support that XYWAV can be dosed with or without food. If warranted, the data obtained from this study would be included to support future label discussions with regulatory agencies.

The target study population is participants with narcolepsy, with or without cataplexy that have remained on a stable regimen of Xyrem for no less than 2 months prior to start of this study, at any prescribed dose (up to a maximum of 9 grams) taken once, twice, or thrice nightly and with no single dose exceeding 6 grams.

An estimated total of 100 eligible participants with narcolepsy will be enrolled into this single-arm study. The total duration of the study is expected to be approximately 17 months, with duration of individual subject participation around 3 to 3.5 months. The study comprises the following phases:

Screening Period (Up to 30 days)

To be eligible for the study, all participants must have been titrated to a tolerable and effective dose and regimen of Xyrem (with or without any concomitant anticitaplectics or stimulants), which shall have remained stable for \geq 2 months prior to entry into study. During the initial Screening period of up to 30 days, all participants will be evaluated for eligibility based on screening assessments ([Section 1.3](#)), with the option to rescreen once ([Section 5.4](#)).

Baseline Period (2 weeks)

Following study entry, participants will remain on same stable dose and regimen of Xyrem during a 2-week Baseline period. Baseline weekly rates of cataplectic attacks and ESS scores (as a measure of EDS) will be determined in this period, in addition to other baseline treatment and safety measures as outlined in SoA ([Section 1.3](#)).

Intervention (Open-Label Conversion and Treatment Optimization) Period (6 weeks)

During the Intervention (Open-Label Conversion and Treatment Optimization) period, participants on a stable dose and regimen of Xyrem will be switched to the same dose (gram-per-gram) and regimen of the study intervention drug (XYWAV). Any concomitant anticitaplectics or stimulants will be maintained as per their current dose and regimen throughout the study.

Once the investigator determines that a stable dose and regimen has been achieved, XYWAV may be taken with or without food. If needed, XYWAV may be titrated to an optimized dose and regimen based on efficacy and tolerability, under the advisement and instruction from the investigator, with the goal to end the period with \geq 2 weeks of optimized therapy on XYWAV.

Safety Follow-up Period

Following the Intervention period, participants will return for a Safety Follow-up visit 2 weeks after the End of Treatment (ET) or Early Discontinuation (E/D) ([Section 1.3](#)). Following the ET or E/D, including during the Safety Follow-up period, it is understood and expected that investigators will determine the appropriate course of care with the participant, and may resume any prescribed medications that were discontinued prior or during the study. There is no plan to monitor participants beyond the 2-week Safety Follow-up period.

Assessments of all study endpoints (as listed in [Section 3](#)) will be summarized descriptively. Formal hypothesis testing will not be performed.

An optional interim analysis may be conducted, without pause in enrollment, as described in [Section 9.5](#). A Data Monitoring Committee is not planned for this study.

4.2. Scientific Rationale for Study Design

The open-label design of Study JZP258-401 is intended to enable descriptive assessments of safety, tolerability, effectiveness and optimization of treatment associated with switching of Xyrem-stable participants to XYWAV.

An estimated total of 100 participants are expected to be enrolled in this study to achieve the study objectives, and further expand the current database of known participants transitioning to XYWAV. In the previous phase-3 pivotal trial (Study 15-006) for XYWAV in patients with narcolepsy, a set of 75 patients switching to XYWAV were sampled. This current study will add another estimated 100 cases, thus expanding the size of the XYWAV-conversion participant database.

Repeated (weekly) visits have been incorporated as part of the study schedule to capture frequent data points as participants proceed through the treatment conversion and optimization process with XYWAV. The frequency and schedule of visits is designed to maximize participant-investigator interaction at critical time points (eg, when initiating conversion to XYWAV) but minimized during periods where participants are expected to be on a stable dose and regimen (eg, during the Baseline period, and the last two weeks of the 6-week, Intervention period).

The Baseline period involving an extended 2-week duration in which participants will remain on their currently prescribed, baseline Xyrem therapy has been included to provide more robust assessment of participant baseline data than provided in Study 15-006. The open-label design is deemed appropriate for this purpose, as efficacy of Xyrem and XYWAV has been previously established.

Specific study endpoints for assessments of safety, tolerability, effectiveness, participant preference, and ease of conversion from Xyrem to XYWAV are described in Section 3 and [Section 8.2-3](#). The key descriptive endpoints for effectiveness, safety, and tolerability include changes in weekly rate of cataplexy attacks (for Narcolepsy Type 1 [NT1]), change in Epworth Sleepiness Scale (ESS) to assess EDS, Patient Global Impression of Change (PGIC), Adverse Events (AEs) and Serious AEs (SAEs), and change in nausea based on Nausea Visual Analog Scale [NVAS]. The treatment optimization endpoints include time to optimized dose and regimen, number of changes from the first dose and regimen to optimized dose and regimen, number of participants dosing fasted versus dosing without regard to food, and timing and characterization of meals relative to dosing. Additionally, exploratory endpoints will include ease of treatment conversion based on Ease of Switching Medication Scale (EOSMS) and medication preference based on Forced Preference Questionnaire (FPQ) assessments.

To decipher the clinical impact of dosing related to food, investigators will instruct participants to initiate XYWAV at the same dose and regimen as Xyrem with the first nightly dose taken at least 2 hours after meal. Once the investigator determines that a stable dose and regimen is established, XYWAV may be taken with or without food. If needed, XYWAV will be titrated to an optimized dose and regimen based on efficacy and tolerability, under the advisement and instruction from the investigator. ([Section 8.1.6](#)).

Collectively, this study will expand the body of knowledge on the overall clinical experience in participants with narcolepsy transitioning from treatment with Xyrem to XYWAV.

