This current study (JZP258-401) is a multi-center, open-label, single-arm, phase 4 trial that seeks to build upon the demonstrated benefits of XYWAV and provide further descriptive evidence of safety, effectiveness, tolerability and treatment optimization in participants switching from Xyrem to XYWAV. The study will include comparative assessments related to treatment-based and exposure-related adverse events (AE), tolerability, and therapeutic effectiveness of disease control between Xyrem and XYWAV. Participants will be switched from Xyrem to XYWAV at the same dose and regimen as Xyrem. Once the investigator determines that a stable dose and regimen of XYWAV is achieved, participants will be allowed to dose with or without food. If needed, XYWAV will be titrated to an optimized dose and regimen based on efficacy and tolerability, under the advisement and instruction from the investigator.

Success in this study will be indicated by seamless switching of the majority of participants from Xyrem to XYWAV, with little or no changes in dose strength or regimen. Additionally, evidence will be provided to support participant preference for XYWAV based on its lower level of sodium, potentially improved tolerability profile, a safety profile typical of oxybate, and similar disease control as participant's current Xyrem dose and regimen. Collectively, these data are expected to expand the knowledgebase of clinical experience in the population of participants with narcolepsy transitioning from Xyrem to XYWAV.

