8.4.2. Method of Detecting Adverse Events and Serious Adverse Events

Care will be taken not to introduce bias when detecting AEs and/or SAEs. Open-ended and non-leading verbal questioning of the participant is the preferred method to inquire about AE occurrences.

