7.2.2. Study Day

The screening period is from Day -30 to Day -1. The 2-week baseline period is Day 1 to Day 14. Participants on a stable dose and regimen of Xyrem will be switched to XYWAV treatment at the beginning of the Intervention (Open-label Conversion and Treatment Optimization) period, starting the night of Visit 3/Day 15 and continue through to the End of Treatment (ET) (Visit 8) or Early Discontinuation (E/D) visit, as applicable.

Study day will be calculated as:

Study Day = (the date of assessment or event - the first day of the baseline period (Visit 2)) + 1 XYWAV Study Day = (date of assessment - date of first dose of XYWAV) + 1

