7.2.3. Visit Windows

Except where specified, all data will be summarized using the CRF visit at which the data was collected. Where data is captured at an Early Termination visit, those data will be summarized with the regular visit at which the assessment would have been captured, relative to the study period during which the participant withdrew. For example:

- If a participant early discontinues during the Baseline Period, i.e. prior to the first dose of XYWAV, then data should be mapped to Visit 3.
- If a participant early discontinues during the Intervention Period, i.e. after at least one dose of XYWAV, then data should be mapped to the next scheduled visit at which those data would have been captured, based on the Schedule of Assessments.

For data captured independent of a CRF visit, eg, Adverse Events, Concomitant Medications and Cataplexy Diary, the following rules will apply:

- If the reported date is on or prior to first dose of XYWAV then the data will be considered to be included into the Xyrem Baseline Period for summaries
- If the reported date is after the first dose of XYWAV while on or prior to the completion of treatment or early discontinuation, then the data will be considered to be included into the XYWAV Intervention Period for summaries.

Unscheduled visits in general will not be mapped (excluded from analyses) when the corresponding scheduled visit is present. Unscheduled visits will only be mapped when the scheduled visit is missing. If more than 1 unscheduled assessments are available, choose the one with the assessment date closer to the target study day specified below, if 2 assessments are equally close to the target day (but on different sides), the latter assessment will be chosen. In addition, unscheduled visits with the assessment date earlier than the date of first dose of XYWAV, or participants early discontinue the study prior to the first dose of XYWAV, the data can only be mapped up to Visit 3. If the assessment date is later than the date of first dose of XYWAV, the unscheduled data should not be mapped to any visit prior to Visit 3.

Study Period	Study Visit	Target Study Day
Baseline	Visit 2	1
Intervention	Visit 3	15

Intervention	Visit 4	22
Intervention	Visit 5	29
Intervention	Visit 6	36
Intervention	Visit 7	43
Intervention	Visit 8	57

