An overall summary on Xyrem-emergent AE and TEAE with following categories will be provided:

- Subjects with any Xyrem-emergent AE/TEAE
- Subjects with any drug-related Xyrem-emergent AE/TEAE
- Subjects with any serious Xyrem-emergent AE/TEAE
- Subjects with any Xyrem-emergent AE/TEAE by severity
- Subjects with any Xyrem-emergent AE/TEAE with outcome as death
- Subjects with any Xyrem-emergent AE/TEAE leading to drug withdrawal
- Subjects with any Xyrem-emergent AE/TEAE leading to drug dose reduction
- Subjects with any Xyrem-emergent AE/TEAE leading to drug dose increase
- Subjects with any Xyrem-emergent AE/TEAE leading to drug interruption

In addition, subject incidence of Xyrem-emergent AEs/TEAEs will be summarized by following:

- SOC and PT
- PT only
- Maximum Severity by SOC and PT
- Drug-related by SOC and PT
- Xyrem-emergent AE/TEAE leading to drug withdrawal by SOC and PT

For data listings, all following will be presented:

- All AEs
- AEs with an outcome of death
- AEs leading to drug withdrawal
- Serious AEs

If a participant has multiple events with the same PT occurring in different periods, the event will be reported for each of those periods. Participant incidence of AEs by SOC and PT tables are sorted by SOCs (alphabetical order) and then by PTs (descending order) within each SOC for the overall frequency. For summaries by PT only, PTs will be sorted in descending order of overall frequency.

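### The parallel Xyrem-emergent AE and TEAE percentages in SAP 10.2 mix drug with length of observation and frequency of questioning; one matched-window table and a footnote would make them readable

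*Protocol*

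**What the plan says.** - **Contact schedule.** Protocol 4.2 explains that participant–investigator interaction is concentrated at conversion and "minimized during periods where participants are expected to be on a stable dose and regimen (eg, during the Baseline period"); it gives the final fortnight of the Intervention period as a second example. SAP 7.2.2 states: "The 2-week baseline period is Day 1 to Day 14". XYWAV starts on the night of Day 15 and runs to Visit 8. SAP 7.2.3 sets target days 1, 15, 22, 29, 36, 43 and 57 for Visits 2 to 8.
- **How AEs are found.** Protocol 8.4.1 ties collection to the contacts in the Schedule of Activities. Protocol 8.4.2 adds: "Open-ended and non-leading verbal questioning of the participant is the preferred method to inquire about AE occurrences". The diaries cover cataplexy, food and dosing, and nausea; none asks about AEs in general.
- **Intent.** The Protocol Introduction (Section 2) announces "comparative assessments related to treatment-based and exposure-related adverse events (AE), tolerability" and disease control between Xyrem and XYWAV.
- **Output.** SAP 10.2: "An overall summary on Xyrem-emergent AE and TEAE with following categories will be provided". The Xyrem-emergent class runs from consent to the first XYWAV dose, so it includes Screening; TEAEs run from that dose to End of Treatment. Incidence is by participant, with no rate per time at risk and no split by onset interval. The denominators also differ (Safety set and XYWAV Safety set).
- **Baseline-only summary.** Protocol 9.4.4 plans Xyrem-emergent AEs both overall and for the Baseline period. SAP 10.2 lists no Baseline-only table, and SAP 7.6 does not record its omission as a change.

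**The concern.** Two percentages under identical row labels will be read as a drug difference. Here the two columns differ in days observed and in how often participants are asked. A brief, mild event is more likely to be remembered and recorded after 7 days than after 14 or 30. Dividing by time at risk would deal with unequal length but not with unequal capture per day.

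The reading matters because Protocol 9.5 allows interim results to be presented externally, and Protocol 4.1 says the data may support label discussions.

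**Working it through.** **1. Reproduce the schedule.** The Schedule of Activities labels Visits 4 to 8 as weeks 3, 4, 5, 6 and 8. Day = 7 × week + 1 gives 22, 29, 36, 43 and 57, which matches SAP 7.2.3. Successive gaps from Day 1 are 14 | 7, 7, 7, 7 | 14 days.

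**2. Length and contacts per window.**

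| Window | Days | Look-back contacts | Days per contact |
|---|---|---|---|
| Xyrem, Baseline only (Visit 2 to 3) | 14 | 1 | 14 |
| Xyrem-emergent, Screening at its 30-day maximum | 30 + 14 = 44 | 2 (Visits 2 and 3) | 22 |
| XYWAV, Visit 3 to 8 | 57 − 15 = 42 | 5 | 8.4 |
| XYWAV, Visit 7 to 8 | 57 − 43 = 14 | 1 | 14 |

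On XYWAV participants are asked 14/8.4 = 1.67 times as often as in Baseline, and 22/8.4 = 2.6 times as often as over the longest Xyrem-emergent window.

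**3. Effect of length alone.** Assume a constant daily hazard, no drug difference, and 10% incidence in 14 days. Then P(42) = 1 − (1 − 0.10)^3 = 27.1%, a ratio of 2.7. For assumed 14-day incidences of 5% and 30% the ratios are 2.9 and 2.2. For the longest Xyrem window, P(44) = 1 − 0.90^(44/14) = 28.2%, so length nearly cancels and contact frequency is what remains. Screening length varies by participant, so the actual Xyrem window lies anywhere between these cases.

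**4. Effect of contact frequency (illustration).** The documents give no recall rate. Assume that recall of a minor event halves every h days. Mean capture over a look-back of T days is c(T) = (1 − 2^(−T/h)) / (T ln 2 / h). The XYWAV average is (28 c(7) + 14 c(14))/42; the 44-day Xyrem average is (30 c(30) + 14 c(14))/44.

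| h (days) | c(7) | c(14) | c(30) | XYWAV / Baseline | XYWAV / 44-day Xyrem window |
|---|---|---|---|---|---|
| 7 | 0.721 | 0.541 | 0.319 | 1.222 | 1.696 |
| 14 | 0.845 | 0.721 | 0.521 | 1.114 | 1.375 |
| 30 | 0.923 | 0.854 | 0.721 | 1.054 | 1.179 |
| 60 | 0.961 | 0.923 | 0.845 | 1.027 | 1.090 |

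These are ratios of recorded events per day when the true rates are equal.

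**5. Both together, Baseline against XYWAV.** With 10% recorded in Baseline, XYWAV incidence is 1 − 0.90^(3r), where r is the XYWAV/Baseline ratio above. For r = 1.027 this is 27.7%; for r = 1.222 it is 32.0%. Length contributes 27.1 − 10 = 17.1 points, and questioning adds 0.6 to 4.9 points.

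**6. A like-for-like pair exists.** Visit 2 to 3 and Visit 7 to 8 are each 14 days with one closing contact. New-onset counting leaves out ongoing events in both. Neither document plans this table.

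**The case against.** The study is descriptive. No test is planned, no AE contrast is specified, and the intent to compare rests on one sentence in the Introduction. Closer contact after a switch is a deliberate choice, explained in Protocol 4.2, and any extra capture counts against XYWAV. Questioning is the preferred method, not the only one: participants may report events themselves, and unscheduled visits are allowed. The tolerability contrast the protocol names, nausea, uses daily NVAS ratings over the last 7 days of each period and so has matched collection. The size depends on an assumed forgetting curve. At an assumed 10% incidence in 100 participants, a 3% to 22% relative excess is 0.3 to 2.2 participants, against a standard error of √(0.10 × 0.90/100) = 3 points.

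Most of this stands, and it limits the point to a modest one. Serious or persistent AEs and the NVAS are little affected. The objection does not make the two columns comparable, and the absence of a test does not stop readers from comparing them.

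Two stronger readings are tempting:

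- A reader might infer that the tables will show an early XYWAV excess followed by a fall in the last fortnight. No planned table splits TEAEs by onset interval, so neither pattern would be displayed.
- A reader might infer that any Xyrem–XYWAV AE statement must rest on the matched fortnights. The documents do not support that: those windows omit early stoppers and the conversion weeks, which are central to the study's objective.

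**Conclusion.** The point holds as a cheap improvement. The schedule, the parallel incidence tables and the comparative intent are all in the documents. Against Baseline only, unequal length is the larger distortion (ratio 2.2 to 2.9 under the stated assumptions). Against the full Xyrem-emergent window at maximum Screening, length is close (44 against 42 days) and contact frequency dominates.

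The direction of the contact effect is towards more recorded brief, mild events on XYWAV. Its size is illustrative only: 3% to 22% per day relative to Baseline for recall half-lives of 60 down to 7 days, and 9% to 70% relative to the 44-day window. None of these figures is an estimate of the bias in this trial.

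The count of contacts assumes AE collection at every scheduled contact. The schedule table is broken in the copy read, so this rests on its AE row and Protocol 8.4.1. Visit windows of up to +3 days can move a weekly gap to about 4 to 10 days without changing the pattern.

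**What to change.** In SAP 10.2:

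1. Add one descriptive table in participants who reach Visit 7: AEs with onset from Visit 2 to Visit 3 (Xyrem) beside AEs with onset from Visit 7 to Visit 8 (XYWAV). Label it a stable-dose comparison that excludes the conversion phase and participants who stopped before Visit 7.
2. List the Baseline-only Xyrem-emergent summary that Protocol 9.4.4 already plans.
3. Keep the full-period TEAE table as the main safety output, with TEAEs before Visit 7 and those of early stoppers visible.
4. Footnote the parallel tables with the days observed and the number of contacts in each window.

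The cost is one new table, one already-promised summary and a footnote, all from data already collected. The visit schedule does not change. The drawback is that the matched table covers a selected group and counts no event that began at conversion and persisted, so it must stand beside the full table and not replace it.
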